## **Ethical consideration**

The study's protocol will be reviewed and approved by the Research Ethical Committee, Faculty of Physical Therapy Kafrelsheikh University.

## **Assessment instruments**

1. . Modified Ashworth scale: to measure the degree of spasticity to enroll children in the study, **Appendix I**.

2. Gross Motor Function Measure 88 (GMFM-88) to measure Gross motor performance. **Appendix II.**
3. Pediatric Balance Scale (PBS) to measure Balance. **Appendix III.**
4. Virtual reality glasses (figure 2).
5. Smart display.
6. Spider cage for suspension (figure 3).
7. Smart phone for virtual reality games.

**Figure 2: virtual reality glasses**

## **Procedure**

### **A. Patients preparation**

1. To start the treatment program, an agreement will be taken from the manager of the outpatient clinics, Faculty of Physical Therapy Kafrelsheikh University.
2. To provide safe and effective treatment, all interventions, evaluation and recording of all measurements at the beginning and at the end of the study will be performed by the primary investigator (the same therapist).
3. All the children parents fitted the inclusion criteria, will be given explanation of the treatment protocol in their understandable language and

they will allow their children to participate after signing a consent form, Appendix IV.

4. All the children demographic and outcome measures data will be collected in especially well-designed sheets, (Appendix V) and (Appendix VI).

## **B. Assessment procedures**

### **1. Evaluation of gross motor performance using GMFM-88:**

The Gross Motor Function Measure (GMFM) 88 will be used to determine the severity of each case and to assess the child's motor performance in five dimensions: lying and rolling (17 items); sitting (20 items); crawling and kneeling (14 items); standing (13 items); and walking, running, and jumping (24 items). All items will be checked and scored before interpretation of child's performance in each dimension. Scores of each dimension will be expressed as percentage of maximum scores for that dimension. Total score will be obtained by averaging percentage scores across the 5 dimensions. Individual dimensions of GMFM-88 can be administered depending on the child's current level of function (41).

### **2. Evaluation of balance using Pediatric Balance Scale (PBS):**

The PBS is a standardized tool for testing balance. The items can be measured within 15 min and do not require the use of specialized equipment. The Pediatric Balance Scale is a modified version of the Berg Balance Scale that is used to assess functional balance skills in school-aged children. The scale consists of 14 items that are scored from 0 points (lowest function) to 4 points (highest function) with a maximum score of 56 points (42).

## **C. Treatment procedures:**

### **1. Treatment protocol in Group A, virtual reality protocol:**

- A specialized VR glasses will be used and VR games application.

- Smart phone used can screen mirroring to lcd display.
- During use of VR glasses therapist observe what child do in the game.
- The child stands in the spider cage at treatment period (figure 3).
- Use 360-degree video.
- The treatment duration will be 30 minutes.
- The treatment protocol will be repeated 3 times per week for 12 weeks.

**Figure 3: spider cage**

## **2. The traditional exercise program (given to both groups):**

- The training program of gross motor performance:

All the tests in gmfm 88 will be used as a treatment program and exercises such as basic rolling, sitting, crawling and walking.

- The selected physical therapy program:

1. Neurodevelopmental approach: aims to facilitate typical motor development and function and to prevent secondary impairments (figure 4).

2. Approximation: aims to control spasticity and stimulate the joint mechanoreceptors (figure 5).

3. Stretching exercise: aims to maintain length and flexibility of shorten muscles (figure 6).

4. Strengthening exercise: aims to improve the functional ability (figure 7).

5. Spider suspension exercise for 30 minutes (figure 8).
5. Gait training activities: aims to improve balance (figure 9).
6. Balance training program: aims to improve balance (figure 10).
  - The treatment protocol will be repeated for 12 weeks.

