## **Statement of the Problem**

This study will be conducted to answer the following research question: Is there any significant effect of virtual reality and physiotherapy in spider cage on gross motor performance and balance in children with spastic diplegia?

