## **Delimitations**

This study will be delimited to:

- 30 children with spastic diplegia with age range from 6 to 12 years are enrolled in the study.
- Children will be randomly allocated into two equal groups; Group A will receive virtual reality and physiotherapy, while Group (B) will receive physiotherapy alone.
- All children will receive three sessions per week for twelve weeks.
- Variables will be evaluated pre and post treatment for all child.

- Gross motor performance will be evaluated using Gross Motor Function Measure 88 (GMFM-88).
- Balance will be evaluated using Pediatric Balance Scale (PBS).

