#### **Sample size calculation:**

Using G-power version 3.1.9.7 for windows and regarding t-test study, alpha level of 0.05, confidence interval 80% and effect size of 1.135 calculated from the previous study of Krishna et al. (43), the total sample size will be 28 children (fourteen in each group), (Figure 1). We will increase number to be 30 children (Fifteen in each group) to avoid any drop out.

To avoid selection bias, the children will be randomly allocated by simple random method via choosing one of two wrapped cards representing the two treatment groups, which are:

- Group (A): will receive virtual reality in addition to the traditional exercise program.
- Group (B): will receive traditional exercise program.

[figure not shown]
[figure not shown]

Figure 1: Sample size calculation in G-power software program.

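### As written, the trial tests the addition of a 30-minute VR session in the spider cage, so the hypothesis and aim should not credit the effect to virtual reality itself

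*Combined protocol and SAP*

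**What the plan says.** Under Treatment procedures, the traditional program is headed as given to both groups, and one of its items is "Spider suspension exercise for 30 minutes (figure 8".

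The Group A protocol is set out separately, with its own setting and dose:

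- "The child stands in the spider cage at treatment period (figure 3"
- "The treatment duration will be 30 minutes"
- "The treatment protocol will be repeated 3 times per week for 12 weeks"
- "During use of VR glasses therapist observe what child do in the game"

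The allocation text under Sample size calculation says that Group A "will receive virtual reality in addition to the traditional exercise program", and that Group B gets that program. Delimitations puts it this way: "Group A will receive virtual reality and physiotherapy, while Group (B) will receive physiotherapy alone". Delimitations also gives every child three sessions a week for twelve weeks, which equalises the number of sessions but not their length. Total session length is not stated for either arm.

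The question is worded in several ways. Statement of the Problem asks: "Is there any significant effect of virtual reality and physiotherapy in spider cage on gross motor performance and balance in children with spastic diplegia". The stated purpose refers to VR delivered in the spider cage. Significance of the Study says that the study examines how effective VR is. The null hypothesis denies an effect of VR on gross motor performance and balance.

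**The concern.** On the plain reading, a Group A child has the whole shared program plus another 30 minutes at each VR session, standing in the cage with the therapist observing. Nothing is scheduled for Group B in that time. A difference between arms could come from the VR content, from the extra supervised standing time, or from both.

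The extra time bears on the outcomes. Ten of the 14 Pediatric Balance Scale items (item 4 and items 6 to 14) are performed standing, and one of the five GMFM-88 dimensions is standing. Standing practice is therefore a plausible alternative explanation of a benefit. If a positive result is reported in the terms of the hypothesis, a clinic might buy VR equipment for a gain that more cage time without VR could also have produced.

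**Working it through.** The plan gives no figure for contact time per arm, so there is none to reproduce. Its sample size does reproduce: a two-sided t-test at alpha 0.05 with effect size 1.135, reading the stated 80% as power, needs 13.22 per arm, hence 14 per arm and 28 in total. This point does not alter that figure.

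**Inputs**

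- VR block: 30 min, 3 per week, 12 weeks (Group A protocol).
- Suspension: 30 min, in both arms (traditional program). Its weekly frequency is not stated there.
- Matched block for Group B: none in the visible text, so 0 min.

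**Excess cage time, A minus B**

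Excess = VR block + (suspension in A - suspension in B)

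- Sessions: 3 x 12 = 36.
- VR block: 36 x 30 = 1,080 min = 18 h per child at full attendance, or 90 min per week.
- Suspension difference: 0, because that program is common to both arms. The result therefore does not depend on how often suspension is given.
- As written: 18 + 0 = 18 h.
- If the VR block is meant to be the shared suspension block: 0 h.

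**How much of the excess is suspension exercise.** The Introduction describes spider therapy as suspension by elastic cords, whereas the VR protocol says only that the child stands in the cage. The suspension part is therefore anywhere from 0 h (standing only) to 18 h (cords used throughout).

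**What the contrast identifies (as written)**

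| Arm | Traditional program | VR | Extra cage time |
|---|---|---|---|
| A | yes | yes | yes |
| B | yes | no | no |

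The VR and extra-time columns are identical. The difference between arms estimates their joint effect, and no covariate or choice of test can divide it.

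**Wording against the contrast**

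| Section | Effect named | Supported by the contrast? |
|---|---|---|
| Statement of the Problem | VR together with physiotherapy in the cage | Yes, as a package |
| Delimitations; allocation text | VR added to the program, against the program | Yes |
| Purpose | VR in its cage setting | Partly: names the setting but not the added time |
| Significance | Effectiveness of VR | Goes further than the contrast |
| Hypotheses | Effects of VR | Goes further than the contrast |

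**The case against.** The strongest reply is that the protocol already defines an add-on trial. The research question, Delimitations and the allocation text all pair VR with physiotherapy, and read beside them the hypothesis can be taken to mean the effect of adding VR. Add-on against usual program is a legitimate design, and a time-matched control would answer a different question. This stands: the design needs no defence, and what remains is the attribution in two sections and, more mildly, in the Purpose.

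The second reply is that there may be no time gap. Both blocks last 30 minutes in the same cage, all children have the same number of sessions, and the two cage figures are missing from the text available. VR might have been meant to run during the shared suspension block. That is possible, but nothing visible says so. The additive wording, the heading that gives the program to both groups and the separate VR dose all point the other way.

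Two stronger readings are tempting and not supported. A reader might infer that the protocol sets out to isolate VR alone. No section says this; the word appears only for Group B's physiotherapy, and the Purpose ties VR to the cage. A reader might also infer that Group A gets 18 extra hours of suspension exercise. The text supports 18 extra hours standing in the cage, with the use of cords unstated.

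**Conclusion.** The point holds in a limited form. As written, Group A is scheduled for 18 h per child of supervised cage time that Group B has no counterpart for. The comparison can therefore support a claim about the added package but not about VR itself. The mismatch is clear in Hypotheses and Significance of the Study and milder in Purpose of the Study.

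This rests on the additive reading of the treatment text and on full attendance. If the two cage blocks are one, the excess is 0 h and the VR wording can largely stand. The resulting bias in GMFM-88 or PBS points cannot be computed from the documents. It would be wrong to conclude that the trial is invalid or its sample size mistaken: the add-on question remains answerable.

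**What to change.** Reword the aim in Significance of the Study and the null hypothesis, and the Purpose for consistency, to refer to *the effect of adding a 30-minute VR session in the spider cage to the traditional program*. Limit any conclusion to that package. This needs no extra children, staff or visits; the cost is a narrower claim.

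If VR was meant to run during the shared 30-minute suspension block, say so in both treatment protocols and specify the same cord set-up and exercises in both arms. Compared with the additive schedule, this removes 15 x 18 = 270 child-hours of cage time from Group A. Without the matched set-up, VR may displace suspension exercise, and the arms would then differ in suspension dose.

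A separate 30-minute cage block without VR for Group B is optional, and worth considering only if a VR-specific claim is wanted. If sessions are one-to-one (assumption), it adds up to 15 x 18 = 270 therapist-hours. That is 15 x 1.5 = 22.5 h a week if all 15 children are treated over the same 12 weeks (also an assumption). The Procedure section has one therapist delivering all interventions, so this would be a real burden.

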**Figure 4: Neurodevelopmental approach**

**Figure 5: Approximation**

**Figure 6: Stretching exercise**

**Figure 7: Strengthening exercise**

**Figure 8: Spider suspension exercise**

**Figure 9: Gait training activities**

**Figure 10: Balance training program**

### **Data collection and statistical analysis:**

Data of all children in both groups will be collected and include:

1. Name, serial number and age (years).
2. gross motor performance pre- and post-treatment with GMFM 88.
3. balance pre and post treatment with PBS.

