## **Significance of the Study**

The current study will be directed to investigate effect of virtual reality on gross motor and balance as the weakness of the trunk muscles and lower limb muscles along with spasticity potentially predispose balance and walking issues of children with bilateral spastic CP (12).

The balance deficits in children with CP are multifactorial. According to the system's model proposed by Woollacott and Shumway-Cook, multiple

systems contribute to postural dysfunction in children with CP. Muscle weakness and stiffness of lower limb muscles account for biomechanical constraints and postural malalignment during standing and functional balancing (13).

Virtual reality is one of the novel technology-based approaches to treat balance and motor function in children with CP. It utilizes the interactive simulations created in computer hardware and software, in which the children find opportunities to engage in environments appearing real to them (14).

After reviewing the available previous published studies, it was found that there is no previous study directly compared between the effects of virtual reality and physical therapy in spider cage on gross motor performance and balance with diplegic children CP children. Both therapeutic modalities were found to induce good clinical outcomes when studied separately, so this study will be conducted to examine the effectiveness of virtual reality.

The greater demand for physical therapy for Paediatrics' signifies the need for more effective, safer and evident therapeutic modalities. The findings of this study will help both; the therapists and the children to save time, effort and reach the best results in concise times.

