## **5.Balance.**

Spastic diplegia, the most prevalent type of CP, is characterized by a wide range of ambulatory outcomes. It affects bilateral lower extremities more than upper extremities in most cases. As a result, walking function and corresponding balance control are impacted (32).

Balance control is important in the performance of most functional skills. Postural balance control in children with CP deteriorates as compared to typically developing children, most likely due to slowed and impaired development of neural motor control mechanisms together with the common secondary musculoskeletal abnormalities (33).

Balance control plays a central role in the motor dysfunction in children with spastic diplegic cerebral palsy. Reduced ability of children with spastic diplegia to adapt the sensory and motor components of postural control to changing task and environmental demands affects their proper response to balance disturbance, the recovery from unexpected threats to stability that refer to reactive balance control, functional deficits and the subsequent limitations in mobility. The amount of time required to recover stability following a balance threat (time of stabilization) and the mean area of centre of mass (COM) displacement per second during balance recovery are increased in these children (34).

Due to poor postural control, the delineation “walking by falling” is especially true for children with CP. A heightened fear of falling can also lead to restriction of activities. Although not all falls can be prevented, those due to poor postural control can be reduced by improving balance performance (35).

Falls may result in pain, injury and disability, and individuals may lose confidence in their ability to perform routine activities. Because a relation has been established between constraints on balance control and functional limitations in children with CP, increased efficiency of postural balance control may be necessary for them to facilitate functional performance (36).

Therefore, many researchers have suggested that balance training should be a crucial component of any rehabilitation program for these children. Such training can modify postural balance control by modulating the amplitude of muscle activities and speeding recruitment of the postural muscles (37).

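### Neither arm has a planned record of adverse events, sessions delivered or reasons for stopping, so the trial could report benefit with no harms data

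*Combined protocol and SAP*

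**What the plan says.** The section *Data collection and statistical analysis* opens with "Data of all children in both groups will be collected and include". Three items follow: name, serial number and age; "gross motor performance pre- and post-treatment with GMFM 88"; and "balance pre and post treatment with PBS".

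The timing is the same elsewhere. *Delimitations* says "Variables will be evaluated pre and post treatment for all child". *Patients preparation*, item 2, says that "evaluation and recording of all measurements at the beginning and at the end of the study will be performed by the primary investigator".

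Item 4 of the same section names the forms: "All the children demographic and outcome measures data will be collected in especially well-designed sheets", that is, Appendices V and VI. Appendix V is a baseline demographic sheet. Appendix VI has two rows (GMFM 88 and PBS) and two dated columns (before and after treatment).

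*Statistical analysis* covers descriptive statistics for demographics, unspecified suitable tests, the significance level and the software. It has no safety summary.

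On treatment, *Delimitations* gives every child three sessions a week for twelve weeks. *Treatment procedures* has Group A stand in the spider cage for a 30-minute VR block, and gives both groups 30 minutes of spider suspension. The therapist is to watch what the child does in the game, but no instruction to record anything follows.

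**The concern.** All planned data come from two assessment dates, while all the treatment happens between them. A site that followed the plan exactly would have no form and no rule for noting that a child fell or nearly fell, was in pain, had a seizure, stopped a session early, missed sessions or left the trial. Such information cannot be rebuilt reliably after week 12.

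Two things would be at stake. First, the report could describe benefit on motor function and balance with nothing on harms or tolerability. Second, *Sample size calculation* raises the total from 28 to 30 for drop-out, yet no sheet records who dropped out or why. A child who left because treatment was not tolerated would appear only as a missing post-treatment score.

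**Working it through.** **1. What the collection tools cover**

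- Data list: identity and age, GMFM-88, PBS.
- Appendix V: demographics and history at entry.
- Appendix VI: 2 scores × 2 dates = 4 scores per child.
- GMFM-88 sheet (Appendix II): a free comments field, but it is completed only when the GMFM is administered.
- Statistical analysis: no safety, attendance or withdrawal summary.

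None of these applies to a treatment session.

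**2. Treatment between the two dates**

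- Sessions per child: 3 per week × 12 weeks = 36 (*Delimitations*, both groups).
- Per arm: 15 × 36 = 540. Whole trial: 30 × 36 = 1,080.
- Scheduled sessions with a planned safety or attendance entry: 0.

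**3. The plan's group size**

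Inputs from *Sample size calculation*: t-test, alpha 0.05, effect size 1.135, and 80%, which the text labels a confidence interval and which I read as power. A two-sided two-sample t-test with the noncentral t distribution gives power 0.793 at 13 per group and 0.824 at 14. The stated 14 per group (28 in total) is reproduced. The planned 15 per group gives 0.851. The group size is not in dispute; it is used here only to size what a log could show.

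**4. What a log could show with 15 children per arm**

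Upper limit for the per-child risk when no child is affected:

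- One-sided 95%: 1 − 0.05^(1/15) = 18.1%.
- Two-sided 95%: 1 − 0.025^(1/15) = 21.8%.
- With 14 children: 19.3% and 23.2%.

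The type of limit must be stated. At a true risk of 20%, no affected child among 15 has probability 0.8^15 = 3.5%, so the one-sided limit excludes 20% and the two-sided limit does not.

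Chance of seeing at least one affected child among 15 is 1 − (1 − p)^15. The documents give no event risk, so these values of p are assumptions:

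| Assumed per-child risk | Chance of at least one affected child |
|---|---|
| 1% | 14% |
| 5% | 54% |
| 10% | 79% |
| 20% | 96% |

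The child is the right unit. Treating 540 sessions as independent would give a one-sided limit of 1 − 0.05^(1/540) = 0.55%, but sessions cluster within 15 children, so that figure would be too optimistic.

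**The case against.** The best defence is that the trial asks only about effectiveness. The research question, purpose and hypothesis contain no safety element. The data list is introduced as what the data include, and it is demonstrably not exhaustive, since Appendix V collects gender and diagnosis, which the list omits. A therapist is present throughout. The consent form and front pages were not available for review. And 15 children per arm would give only descriptive safety data.

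Most of this stands, and it rules out several stronger readings that a reader might infer:

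- *That events would be lost.* The documents support only that they would not be systematically recorded in the visible text. A consent form that mentions risks would not replace data collection.
- *That the documents themselves name VR or cage hazards.* They do not. "Falls may result in pain, injury and disability" describes falls in children with cerebral palsy generally. Pain and fatigue appear in the literature review as consequences of inactivity. Seizure history is an exclusion because it may hinder assessment and treatment. The introduction describes the cords as supportive. These passages make the events relevant to this population; they do not attribute them to the intervention.
- *That the trial promises a safety answer.* The remark in *Significance of the Study* that demand "signifies the need for more effective, safer and evident therapeutic modalities" is background. The reason given there for the trial is to examine effectiveness.
- *That the gap is confined to the VR arm, or that recall of events would be uneven between arms.* Both groups receive suspension, the same therapist performs all interventions, and no recall at week 12 is planned.

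What the defence does not supply is any form, rule or summary for harms, attendance or withdrawal.

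**Conclusion.** The point holds as an omission in intact text, equal in both arms: no planned safety, delivery or withdrawal record over 36 sessions per child, against four scores per child at two dates. The consequence is that the trial could report benefit with no harms data and could not describe the treatment delivered or why children left.

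It does not affect the planned comparison of GMFM-88 and PBS, and it is not a failure to meet a stated objective. It is a worthwhile, inexpensive improvement rather than a flaw in the main analysis.

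This rests on two conditions: that no session or safety form exists in the pages not available for review, and that the 36 sessions in *Delimitations* apply to both groups as written. The sample-size limits in the working bound any safety claim even after correction. A clean log in 15 children would still be compatible with a per-child risk of roughly one in five.

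**What to change.** - **Appendix VI:** add a brief per-session log, identical in both arms and completed from one fixed question each session, up to the post-treatment assessment. Fields: session given; minutes delivered; stopped early and why; fall or near-fall; pain or injury; fatigue; seizure; other complaint. Add one entry per child for withdrawal and its reason.
- **Data collection list:** add a fourth item, *adverse events and sessions delivered, from the session log*.
- **Statistical analysis:** add a descriptive table by arm giving the number of children with each event, with exact 95% intervals and no formal test, plus sessions delivered and withdrawals with reasons.
- **Interpretation:** state that no affected child among 15 gives an upper limit of 21.8% (two-sided 95%) or 18.1% (one-sided 95%), and that no claim of safety for VR will be based on this sample.

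Cost: one short form per session and one table. No extra visits, staff or children are needed. The downside is slightly more paperwork and a less favourable safety statement. The log sets no rule for managing events; it only records them.
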